7.1.1 Design Rationale

Subjects

- Only CI recipients implanted with the CI500 series, CI600 series or Freedom series CIs in one or both ears are included as the CDI tool only supports these CIs.
- Hearing ability and the MAPs undergo significant changes in the first months after implantation. Thus,
 CI recipients with at least three months experience with their CI will be enrolled so that any changes in their hearing function do not act as confounding variables.
- Only adult CI recipients rather than children have been chosen as the study population due to their
 ability to compare MAPs, in and outside of the booth. Additionally, performance benefits achieved by
 adults can generally be extrapolated to younger age groups, avoiding the need to recruit this
 vulnerable population.
- Only subjects who are able to score 20% or more for English CNC words presented at 60dB SPL RMS with CI alone in the test ear will be recruited to avoid floor effects.
- Only subjects willing and able to provide written informed consent will be enrolled to be compliant with ISO 14155.
- Investigator site personnel directly affiliated with this study and/or their immediate families; immediate family is defined as a spouse, parent, child, or sibling or Cochlear employees or employees of Contract Research Organizations or contractors engaged by Cochlear for the purposes of this investigation will be excluded to avoid enrolment of a vulnerable population.
- Only subjects with all 22 electrodes active in the MAP used regularly will be enrolled as all 22 electrodes are required to create a MAP with dual-electrode mode that is comparable across subjects.

Blinding

- Blinding of the study subject will be undertaken, to reduce any bias. Subjects will not be told which MAP will be loaded in the sound processor for take home use and which MAP order to be tested at Visit 2 and Visit 3.
- There will be no blinding of the study investigators.

Visit window

The stimulation rate and dual-electrode mode is likely to be novel to the study subjects. Subjects will
be asked to use MAPs with 900Hz (default & LP1) and 500Hz (LP2 & LP3) for at least four weeks so
that they have sufficient experience with the MAP prior to the speech perception tests with those
MAPs.

Outcome measures

CNC words: Speech perception in quiet will be measured using recorded CNC monosyllabic words
(Peterson & Lehiste, 1962) at 60dBSPL from S0 position. CNC words in quiet at 60dB SPL presentation

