7.2.6 Criteria and Procedures for Subject Withdrawal

Subjects can decide to withdraw from the investigation at any time. The Investigator shall ask the reason(s), however subjects have the right to withhold their reason if preferred. The reason for withdrawal should be documented in the subject's source files and the case report form (CRF), if provided.

The Investigator or Sponsor may also decide to withdraw a subject from the clinical investigation or stop the use of the investigational device if it is considered to be in the subject's best interests.

Subject withdrawal may be for any of the following reasons:

- Adverse Event (AE)
- Device Deficiency (DD)
- CIP or GCP deviation
- Subject withdrew consent
- Subject lost to follow-up
- Subject death
- Sponsor decision
- Investigator decision
- Other (specify)

If subject withdrawal is due to problems related to the IMD safety or performance, the Investigator shall ask for the subject's permission to continue in safety follow up (for example, adverse events and device deficiencies) until their scheduled End-of-Study visit.

If a subject is lost to follow-up, every possible effort must be made by the study site personnel to contact the subject and determine the reason for discontinuation. At least 3 separate attempts taken to contact the subject must be documented.

Participating subjects who are withdrawn/discontinued before the data for primary and secondary endpoints have been collected, may be replaced to meet the minimum sample size criteria or to maintain counterbalancing between the groups.

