7.2.7 Randomisation Procedures

Subjects will be randomly allocated to one of four groups. Programming of sound processors for take home use and test order during visits 2 and 3 will be performed as per the randomisation table (Table 4).

Table 4: Randomisation table

	Take home programs	Visit 2 test order	Take home programs	Visit 3 test order
Group 1A	P1: Default	Test 1: Default	P1: LP2	Test 1: LP2
	P2: LP1	Test 2: LP1	P2: LP3	Test 2: LP3
Group 1B	P1: LP1	Test 1: LP1	P1: LP3	Test 1: LP3
	P2: Default	Test 2: Default	P2: LP2	Test 2: LP2
Group 2A	P1: LP2	Test 1: LP2	P1: Default	Test 1: Default
	P2: LP3	Test 2: LP3	P2: LP1	Test 2: LP1
Group 2B	P1: LP3	Test 1: LP3	P1: LP1	Test 1: LP1
	P2: LP2	Test 2: LP2	P2: Default	Test 2: Default

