- AuSTIN sentence test: Both recorded speech and noise (adaptive four talker babble noise) will be presented from 0 degrees azimuth (S0N0). The signal level will be fixed at 65 dB SPL. One practice list will be administered at the beginning of the session to overcome learning effects. Two lists with 20 sentences each will be administered per condition. If the standard deviation (SD) for any list exceeds 4.12, then the run will be considered as invalid and additional list will be administered. The contralateral ear will be plugged.
- Loading MAPs to processors: CDI Tool will be used to load the test MAPs into a study sound processor for take home use as per the randomisation table (Table 4).
- **Issue of SSQ12:** The SSQ12 questionnaire will be issued, and the subjects will be counselled on how to complete the questionnaire as needed.
- **Standard CRFs:** CRFs including concomitant medications, adverse events, device deficiencies and device exposure will be completed.

CIP Number: CLTD5853

Take home use:

- Subjects will be asked to use two MAPs for four weeks. The subjects will be asked to use P1 on day 1,
 P2 on day 2, P1 on day 3 etc.
- Subjects will be asked to complete the SSQ12 in the fourth week of take home use.

Visit 3:

- Collection of SSQ12:
- Acclimatization: Subjects will be asked to use the specified test MAP for a period of minimum 10
 minutes and listen to live or recorded speech to acclimate to the two conditions prior to speech
 perception testing. Contralateral device will be turned off (if applicable).
- **SAR:** The subjects will be asked to provide responses to the questions in the SAR as soon as they have switched to the new MAP at the end of the acclimatisation period.
- **CNC word test (60dB):** Two lists with 50 words each will be administered per condition. The contralateral ear will be plugged. The test order will be determined using the randomisation table (Table 4)
- AuSTIN sentence test: Both recorded speech and noise (adaptive four talker babble noise) will be
 presented from 0 degrees azimuth (S0N0). The signal level will be fixed at 65 dB SPL. One practice list
 will be administered at the beginning of the session to overcome learning effects. Two lists with 20
 sentences each will be administered per condition. If the SD for any list exceeds 4.12, then the run will
 be considered as invalid and additional list will be administered. The contralateral ear will be plugged.

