9.4 Sample Size Determination

This study is a non-inferiority design, and sample size calculation was based on non-inferiority tests for CNC word scores and SRT (Speech Recognition Threshold) scores.

To reject the null hypothesis of inferior CNC Words correct in quiet (60 dB) scores, a sample size of 14 will provide more than 90% power to detect non-inferiority of CNC word scores and 90% power to detect non-inferiority of SRT with the following parameters:

CIP Number: CLTD5853

- A clinically important difference value of 10% for CNC words and 1 dB SRT for AuSTIN. This margin is based on clinical consensus.
- A SD of change or difference scores of 6.914% for CNC words and 1.037 dB for AuSTIN. The expected standard deviation of difference scores for CNC words was based on a previous dual electrode mode study (CRC 5523) on the relevant endpoints.
- A significance level $\alpha = 0.025$ (one-tailed).

There are four subgroups in the randomisation table (Table 4); to ensure equal number of subjects in each subgroup a minimum of sample size of 16 (or a higher multiple of 4) is required. Twenty subjects will be enrolled in total to allow for any unforeseen subject withdrawal with a possible attrition rate of 25% and to ensure equal number of subjects in the four subgroups. Replaced subjects will be recruited if the minimum sample size of 16 could not be met due to subject withdrawal or loss to follow up.

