9.5 Analysis Populations

The analysis of the primary endpoint will be based on the Intent-To-Treat (ITT) and Per Protocol (PP) analysis populations in order to support a conclusion of non-inferiority. The inclusion of both ITT and PP populations has been chosen to assess the robustness of the study results and the consistency of the study measures under different analysis populations.

This study has a non-inferiority design; therefore, the primary analysis will be based on the PP population.

For cases in which the ITT and PP populations lead to the same conclusions and final interpretations about the LP MAP effect, the results will be considered to not be influenced by underlying factors such as missing data and protocol deviations, and the results would be considered to be robust and consistent under different analysis populations. A statement to reflect this will be included in the CIR.

For cases in which the ITT and PP populations lead to different final interpretations or conclusions, all of the results will be reported and the differences in outcomes will be identified and explored.

Intent-to-Treat Population

The Intent-to-Treat Population will include all subjects who receive the MAPs and have at least one set of paired MAPs measurements from any endpoint, regardless of protocol deviations and missing data.

Per Protocol Population

The Per Protocol Population will include all subjects who receive the MAPs and have at least one set of paired MAPs measurements without major protocol deviations from any endpoint. Major deviations will be defined and documented at the clean file meeting before data base lock.

It is possible that a LP MAPs has not been administered in the intended counterbalanced order of presentation. It is also expected that the sequence and period effects are minimal in this study if any. This study is not a full cross-over design, so period and sequence effects will not be assessed, without the consequence to bias the study conclusion.

Safety Population

The Safety Population will include all subjects who used the investigational MAPs. The Safety Population will be used for the safety data analysis.

CIP Number: CLTD5853

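### Section 9.5 rules out bias from period and sequence effects without support, yet secondary endpoints 1–4 compare different visits; analysing them by randomised sequence is cheap and mainly protects power

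*Combined protocol and SAP*

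**What the plan says.** Section 7.2.7: "Subjects will be randomly allocated to one of four groups". Under Table 4, Groups 1A and 1B are tested with Default and LP1 at Visit 2 and with LP2 and LP3 at Visit 3. Groups 2A and 2B have the reverse order.

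Section 9.5 on visit and order effects:
- "It is also expected that the sequence and period effects are minimal in this study if any"
- "so period and sequence effects will not be assessed, without the consequence to bias the study conclusion"
- "It is possible that a LP MAPs has not been administered in the intended counterbalanced order of presentation"

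The only reason offered is that the design is not a full cross-over.

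Section 9.6.1 tests non-inferiority with the 95% CI of the mean paired difference, with no term for sequence or period. Section 9.6.2 applies the same method to the secondary endpoints. Section 9.6 puts these tests in a fixed order for labelling claims and stops formal testing at the first failure.

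On balance, section 9.4 aims for equal subgroups, but its replacement rule depends on the total: "Replaced subjects will be recruited if the minimum sample size of 16 could not be met". Section 7.2.6 makes replacement for balance optional: withdrawn subjects "may be replaced to meet the minimum sample size criteria or to maintain counterbalancing between the groups".

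The design does limit visit effects. Under section 7.1.1 subjects will "be asked to use MAPs with 900Hz (default & LP1) and 500Hz (LP2 & LP3) for at least four weeks". Section 7.3.2 adds at least 10 minutes' acclimatisation and, for AuSTIN, "One practice list will be administered at the beginning of the session to overcome learning effects". No practice list is described for CNC words.

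**The concern.** Secondary endpoints 1–4 set results from visits at least four weeks apart against each other. Any general change between visits (practice, familiarity, testing conditions) enters the paired difference with one sign in Groups 1A/1B and the opposite sign in 2A/2B. That the study is not a full cross-over does not protect a contrast that spans two periods. No shift size or source is given, and the planned analyses would yield no period estimate against which to check the expectation.

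Two consequences follow. If unequal numbers are analysed in the two visit orders, the mean is shifted for that split. If numbers are equal, the mean is unbiased, but the opposing shifts inflate the SD and widen the interval. A failure at secondary endpoint 2 (SRT, LP2 against LP1) would also end formal testing of LP3. The primary endpoints compare two MAPs at the same visit, so a visit shift cancels there.

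**Working it through.** **Inputs from section 9.4.** One-sided alpha 0.025; margins 1 dB (SRT) and 10 points (CNC); SD of differences 1.037 dB and 6.914 points; minimum analysed n 16, enrolled 20. Assumed: true difference 0 for power; visit shifts p of 0.25, 0.5 and 1.0 dB; 1.037 dB read as the SD within a visit order.

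**The plan's own figure.** Paired t test (noncentral t), n=14: SRT power 91.5%, CNC 99.9%. At n=13 SRT power is 89.0%. The stated 90% and more than 90% at n=14 are reproduced.

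**Model.** Let p be the Visit 3 minus Visit 2 shift. The paired difference (LP2 or LP3 minus LP1) is τ + p + error in 1A/1B (n1 subjects) and τ − p + error in 2A/2B (n2 subjects), with N = n1 + n2.

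- Unadjusted: the mean has bias p(n1 − n2)/N, and the expected sample variance is σ² + p²·4n1n2/[N(N−1)], on N−1 df. At 8/8 and p = 0.5 the bias is 0 and the SD rises to √(1.0754 + 0.25×1.0667) = 1.158 dB. At 0.5 dB the bias is 0.0625 dB for 9/7 and 0.125 dB for 10/6.
- Adjusted: half the sum of the two sequence means, SE = (σ/2)√(1/n1 + 1/n2), on N−2 df. The result does not depend on p. At 8/8 the SE is 0.259 dB.

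**SRT power, balanced 8/8**

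| Shift | Unadjusted | Adjusted |
|---|---|---|
| 0 | 95.0% | 94.8% |
| 0.25 dB | 94.2% | 94.8% |
| 0.5 dB | 91.8% | 94.8% |
| 1.0 dB | 78.9% | 94.8% |

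**SRT power averaged over random losses from 10/10.** Four losses leave 16, the lowest total before the replacement rule of 9.4 applies. The split is then 8/8 with probability 41.8%, 9/7 or 7/9 with 24.8% each, and 10/6 or 6/10 with 4.3% each.

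| Losses | Shift | Unadjusted | Adjusted |
|---|---|---|---|
| 0 | 0.5 dB | 97.0% | 98.3% |
| 2 | 0.5 dB | 94.8% | 96.9% |
| 4 | 0.25 dB | 94.2% | 94.5% |
| 4 | 0.5 dB | 91.4% | 94.5% |
| 4 | 1.0 dB | 77.4% | 94.5% |

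**Error rate.** Averaged over 0 to 4 losses, unadjusted false non-inferiority for SRT is 2.2–2.3% at 0.25 dB, 1.5–1.7% at 0.5 dB and below 0.7% at 1.0 dB, so the planned test is conservative. Under simple randomisation at n=16 (section 7.2.7 describes no blocking) it is 2.5%, with power at 0.5 dB of 90.1% unadjusted and 93.1% adjusted.

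**Particular splits at n=16, 0.5 dB.** An unfavourable 10/6 gives power of 83.3% against 93.4% adjusted. A favourable 10/6 gives false non-inferiority of 4.4% against 2.5%. A favourable 9/7 gives 2.6%, and its maximum over the shifts tried is 2.9%, at 0.25 dB.

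**Break-even.** Adjusting gains SRT power once the shift exceeds about 0.13 dB at 8/8, or about 0.19 dB averaged over four random losses.

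**CNC.** At 8/8 unadjusted power is still 99.1% with a 7.5-point shift. A favourable 10/6 with a 5-point shift would give 4.4% error, as for SRT.

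**The case against.** The strongest reply is that the clause is largely right in effect. Expected bias is zero, average error does not exceed about 2.5%, and the design aims at equal groups, where bias is exactly zero. Error inflation needs both a shift and a favourable imbalance, and a favourable 10/6 split has probability of only 4.3% given four losses. At 0.5 dB, average power stays above the planned 90%. Below about 0.13 to 0.19 dB adjusting loses a little power, and only a shift as large as the margin does serious damage. All of this stands and is why the point is minor. It does not make the stated reason valid.

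Second, the SD may already contain visit variation. Section 9.4 does not say, and names a source only for the CNC figure. If 1.037 dB is the total SD with a 0.5 dB shift inside it, the within-sequence SD is √(1.037² − 0.5²) = 0.908 dB. Power at 8/8 is then 96.6% unadjusted and 98.3% adjusted; over four random losses, 96.2% and 98.2%. Planned power is not threatened on that reading, but adjusting still does better.

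Third, adjustment removes an additive visit shift but not differential carry-over, which this design cannot separate. The period estimate is therefore an imperfect check. This stands.

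Fourth, a test-order effect within a visit would enter the primary contrast with opposite signs in the A and B groups, at a similar variance cost. That is fair, but it is a different effect from the visit shift considered here.

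**Conclusion.** The concern holds, at minor severity. The no-bias statement is unsupported for secondary endpoints 1–4, because they are between-visit contrasts and equal sequence numbers are an aim rather than a guarantee. The practical cost is SRT power: about 3 points at a 0.5 dB shift and 17 points at 1.0 dB, averaged over four random losses. Inflated error is confined to uncommon favourable splits. CNC power is barely affected, and the primary conclusion is unaffected by a visit shift. Secondary tests are formally reached only if both primary tests succeed. The sizes rest on assumed shifts, an additive visit effect, a true difference of zero for power, and reading 1.037 dB as a within-sequence SD. Confidence is medium because the documents give no shift size.

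**What to change.** In section 9.5, delete the claim that the conclusion cannot be biased and the statement that period and sequence effects will not be assessed.

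In section 9.6.2, pre-specify for secondary endpoints 1–4:
- as the basis for non-inferiority, the equally weighted mean of the two randomised-sequence means (1A/1B and 2A/2B), with pooled within-sequence variance and its 95% CI;
- the period estimate with its 95% CI and the number analysed per sequence, noting that differential carry-over cannot be separated from it;
- as sensitivity analyses only, an analysis by the order actually given, and a test-position adjustment for LP2 against LP1. In Table 4, LP1 and LP3 share the same test position in every group, so that contrast does not need one.

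Leave the primary analysis as planned.

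The cost is a protocol amendment with ethics committee notification (section 18), and written approval if it is classed as substantial (section 16). No subjects, visits or data are added. If there is no shift, SRT power at n=16 falls from 95.0% to 94.8% at 8/8, 94.4% at 9/7 and 93.4% at 10/6. At 10/10 it goes from 98.32% to 98.27%.

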5.1 Identity and Description of the Investigational Medical Device (IMD)

The IMD for this investigation is dual-electrode mode configuration of stimulation mode in the firmware of the Nucleus 7 (CP1000), Nucleus 8 (CP1110) and Kanso 2 (CP1150) sound processors outside of the functionality of the commercial system. Dual-electrode mode programs will be created using research software called Cochlear Device Interface Tool (CDI Tool). The investigational ACE MAPs include changes in electrical stimulation parameters such as stimulation rate, PW, stimulation mode and IPG listed in Table 2. This investigational MAPs are used solely for the purpose of clinical investigation. Figure 3 shows a screenshot of the CDI Tool software.

Figure 3: Screenshot of Cochlear Device Interface Tool (CDI Tool).

The clinical hardware used in this study includes a computer with the research CDI Tool software, a commercially available programming pod, and a commercially available CP1000, CP1110 and CP1150 sound processor. The computer is connected to the programming pod, which is then connected to the sound processor.

The development of the research tool (CDI) followed a design control process that is part of Cochlear's ISO13485 compliant quality management system. The research tool has been verified for safety and technical correctness before use in a human trial. The research software tool underwent safety and performance testing according to Cochlear product risk management procedures, in accordance with EN ISO 14971, Medical devices – Application of risk management to medical devices (ISO 14971, 2004) standard. The overall residual risks associated with the investigational devices are acceptable. All risk reduction measures shown in the essential requirements document have been implemented into the final design and verified to be effective.

Subjects will use the MAPs created using the research tool exclusively for the duration of the study. The research tool will be clearly labeled as such on the personal computer. The build number will be documented in the tracking forms, such as the Software Tracking Form (1302326), as mentioned in section 12 of this document. The investigator will undergo training on how to use the IMD and the research tool, and the completion of this training will be recorded in a training log.

5.2 **Identity and Description of the Comparator**

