The commercially available ACE coding strategy programmed with the default 900Hz stimulation rate will serve as the comparator. The investigator will use CDI Tool to create the comparator MAP. MAPs will be written to the commercially available CP1000, CP1110 and CP1150 sound processors.

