7.2.5 Recruitment and Study Duration

The following subject status definitions apply:

- Enrolled: A subject that has signed the Informed Consent form for the study.
- Screen Fail: An Enrolled subject that has been determined to not meet one or more eligibility criteria.
- Participated: Subjects who have met eligibility criteria and have commenced visit 1 procedures.
- Discontinued: An Enrolled subject who withdrew consent, was discontinued by the Investigator or Sponsor before the expected End of Study visit or lost to follow-up. Discontinued subjects may still have safety follow up data collection until their scheduled End of Study visit, for reasons described in section 7.2.6.
- Completed: Enrolled subjects who complete the required treatment and visit schedule.

The recruitment period for the clinical investigation is estimated to be seven months from the time of first subject consent to recruitment of the last subject. This is to allow the replacement of any subjects who withdraw from the study.

The expected minimum duration of each subject's participation in the clinical investigation, is eight weeks, from the time of informed consent through to the End of Study when devices are returned. The anticipated total duration of the clinical investigation is 12 months.

CIP Number: CLTD5853

Clinical Investigation completion is last subject last visit. In the event of an ongoing SAEs/SADEs at the time of this last visit, the clinical investigation completion will be extended for a further 30 days, or until resolution or stabilisation of the event, whichever comes first.

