7.3.2 Performance/Effectiveness

Section 3 shows the overall schedule of events to be followed in this study. Figure 4 shows a simple schematic of the study procedures. Below each visit procedures are provided in greater detail. The subjects will be randomly allocated to groups 1A, 1B, 2A or 2B.

Visit 1:

- Mapping: Four MAPs using parameters listed in Table 2 will be created. The default MAP will be created by measuring T-levels on electrodes 22, 16, 11, 6, 3, and 1. If required, additional T-levels may be measured by the clinician. The Hughson-Westlake method will be used for T-level measurement, aiming for two out of three detections on an ascending run with step sizes of 2 CL up and 4 CL down. Two beeps will be used to determine the T-levels. The C-level profile will use the T-level profile as the starting point. C-levels will be raised globally in live mode until ongoing conversational speech is comfortably loud. The C-levels will be balanced in overlapping groups of three channels. Additional T/C level modifications may be made by the clinician to address any sound quality issues. The T and C levels from the default MAP will be converted to create the LP1, LP2 and LP3 MAPs. For LP3, the T and C levels for each dual channel will be configured to be an average of the two single electrodes comprising the channel. The clinician may change the levels as required to ensure that the LP MAPs are acceptable and have the same loudness as the default MAP by global C-level adjustments and ensuring loudness balance across channels. Loudness balancing will be performed to ensure all MAPs are equally loud. The investigators will be provided hands on training by the sponsor on the use of CDI Tool research software for the creation of the MAPs.
- Clinician log: The clinicians creating the different MAPs will be asked to complete a log (Appendix 2) to record the steps undertaken during creation and optimisation of the different MAPs. The log will capture the clinician's action and the feedback from the CI recipient. To aid in the completion of the log, screen recording with audio recording will be captured.

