11.1 Definitions

11.1.1 Adverse Event

An adverse event (AE) is any untoward medical occurrence, unintended disease or injury, or untoward clinical signs (including abnormal laboratory findings) in subjects, users or other persons whether or not related to the medical device or the procedures required for implant or use, and whether anticipated or unanticipated.

CIP Number: CLTD5853

- NOTE 1: This definition includes events related to the medical device or the comparator device.
- NOTE 2: This definition includes events related to the procedures involved.
- NOTE 3: For users and other persons, this definition is restricted to events related to the use of medical devices.

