11.2 Recording and Handling of Adverse Events

Subjects shall be carefully monitored during the clinical investigation and the investigator should enquire about AEs at investigation visits.

All AEs will be recorded from the time of first use/contact with the IMD and/or comparator. AE recording will continue for each subject until completion of their End of Study visit. Ongoing SAEs, SADEs and/or AESI will be followed for 30 days, or until resolution or stabilisation of the event, whichever comes first.

Source notes should indicate the evaluation for AEs, even if there was none to report. All required AEs will be reported if observed, even if anticipated and/or acknowledged as a risk factor in the consent.

All AEs will have the following information documented: start and stop dates, action taken, outcome, severity and investigators opinion on the potential relationship to the IMD and/or comparator and study procedures. If an AE changes in severity, the most severe (highest) grade will be captured for that event on the Adverse Events CRF.

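### The Safety Population (9.5) is narrower than the adverse-event recording trigger (11.2), so a subject exposed only to the default MAP is recorded but left out of the safety summaries

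*Combined protocol and SAP*

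**What the plan says.** Section 9.5 defines the safety set in one sentence: "The Safety Population will include all subjects who used the investigational MAPs". The next sentence makes it the set for all safety work: "The Safety Population will be used for the safety data analysis". No other population is named for safety.

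Section 11.2 sets the start of recording: "All AEs will be recorded from the time of first use/contact with the IMD and/or comparator". Note 1 in 11.1.1 adds: "This definition includes events related to the medical device or the comparator device".

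Section 5.2 says which MAP is the comparator: "The commercially available ACE coding strategy programmed with the default 900Hz stimulation rate will serve as the comparator". Section 5.1 describes the investigational ones: "The investigational ACE MAPs include changes in electrical stimulation parameters such as stimulation rate, PW, stimulation mode and IPG listed in Table 2".

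Section 7.3.2 (Visit 1, Mapping) gives the order of fitting. The default MAP is built first, with C-levels raised in live mode. Then: "The T and C levels from the default MAP will be converted to create the LP1, LP2 and LP3 MAPs".

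Section 7.1 says safety will be assessed by recording and summarising all adverse events, adverse device effects and device deficiencies. Section 9.7 reports the proportion of subjects with at least one event, by intervention group, and separately the number and proportion who discontinued an intervention because of an event.

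**The concern.** Recording starts with exposure to either kind of MAP, but analysis requires exposure to an investigational one. Someone exposed only to the comparator therefore meets the first rule and fails the second. The fitting order makes this possible, because at Visit 1 every subject is stimulated through the default MAP before any LP MAP exists.

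Section 8.3 names uncomfortably loud stimulation as a risk of programming, and says that non-auditory stimulation is controlled during fitting. An event in the default step is therefore conceivable.

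At stake is the completeness of the descriptive safety tables. Whether such a subject is left out depends on stopping early. The omission is therefore not random, and it can only lower the count of discontinuations due to an event. The tables would also fall short of the aim in 7.1 of summarising all events.

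**Working it through.** The plan states no figure on this point, so there is nothing to reproduce. The check sets the definitions side by side and then illustrates the effect with simple proportions.

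**Step 1: who is in which set, by how far the subject gets at Visit 1**

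| Last exposure before leaving | Events recorded (11.2)? | In Safety Population (9.5)? |
|---|---|---|
| No stimulation with a study MAP, no device contact | No | No |
| Default MAP live, no LP MAP activated | Yes (comparator) | No |
| At least one LP MAP activated during fitting | Yes | Yes, if *used* includes activation during fitting |
| Take-home use of an LP MAP | Yes | Yes |

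The two rules part in the second row. A subject who has an event in default fitting and then goes on to an LP MAP is in the Safety Population, and that event is counted. The gap therefore needs both an event in the default step and an exit before the first LP activation.

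**Step 2: pooled illustration**

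Inputs: N = 20 planned subjects (9.4). One comparator-only subject with an event is an assumption. N = 20 starting Visit 1 is also an assumption, because 7.2.5 defines enrolment by signed consent. No replacement is assumed. Let k be the number of other subjects with an event.

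- All exposed subjects: (k + 1)/N. Set as defined in 9.5: k/(N − 1).
- N = 20, k = 0: 1/20 = 5.0% against 0/19 = 0%.
- N = 20, k = 1: 2/20 = 10.0% against 1/19 = 5.3%.
- N = 16 (the minimum in 9.4), k = 0: 1/16 = 6.3% against 0/15 = 0%.

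**Step 3: the same subject in the layout of 9.7**

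Section 9.7 reports by intervention group, not pooled. Take N = 20 and k = 0, and assume that the other 19 are exposed to all four MAPs. If events are assigned to the MAP in use at onset:

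- Default: 1/20 if the subject is counted, 0/19 under 9.5.
- LP1, LP2, LP3: 0/19 each under either rule, because the subject was never exposed to them.
- Discontinuations due to an event: 1 if the subject is counted, 0 under 9.5.

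The omission therefore affects the default column and the discontinuation count. It does not change the reported incidence for any LP MAP.

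**The case against.** The strongest reply is that the gap is very small. All four MAPs are made in one visit. Subjects already use a 900 Hz ACE MAP (inclusion criterion 4), so default fitting is close to their usual care, and 8.3 says that the fitting risk does not exceed that of normal handling. The event would not be lost: it goes into the CRF, the sponsor reviews all safety data (11.4.2), and the Clinical Review Board reviews reported device effects and deficiencies (8.4). All of this stands, and it limits the importance of the point. It does not put the subject into the 9.7 tables.

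A second reply is that the default MAP may itself count as investigational. Section 12 lists the CDI Tool and the loaner processors as investigational devices, and 5.2 has the CDI Tool create the comparator MAP. The synopsis, however, says the comparator is created with Custom Sound, so the documents disagree on the software. Section 7.3.2 also speaks of four MAPs with Table 2 parameters, while 4.3 says that Table 2 lists three combinations. This shows ambiguity. But 9.5 refers to investigational MAPs, not devices. No section calls the default MAP investigational, and 5.2 names it the comparator.

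A reader might also infer more than the documents support:

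- *That the rule removes every subject who stops because of a fitting risk.* It does not. The 8.3 risks apply to all programming in the study, and a subject who stops after an LP MAP has gone live has been exposed to one.
- *That* used *means take-home use, so that events in LP fitting are lost too.* Section 9.5 does not say so, and the example entries in Appendix 2 show LP3 made live, with recipient responses, while the MAP is being created.
- *That replacement under 7.2.6 hides such events.* Replacement there serves sample size and counterbalancing. It deletes no safety data.

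**Conclusion.** The mismatch holds on the plain text. Section 9.5 is narrower than the trigger in 11.2 and than the aim in 7.1, and a recorded event and a discontinuation can be missing from 9.7 as a result. It concerns only subjects who have an event in default fitting and leave before any LP MAP is activated.

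The point is minor. The documents give no rate for such exits, safety oversight during the trial is unaffected, and no hypothesis test or efficacy result changes. The contrast of 0/19 with 1/20 should not be read as the incidence that the plan would report. It is a pooled illustration that assumes one such subject among 20 starting Visit 1, no other events and no replacement. In the by-group layout only the default column and the discontinuation count would move.

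**What to change.** In 9.5, define the Safety Population as all subjects with first use of or contact with the IMD and/or the comparator, and state that stimulation during Visit 1 fitting counts. This is the plan's own trigger from 11.2.

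In 9.7, state that each event is assigned to the MAP in use at onset, and that the denominator for each MAP is the number of subjects exposed to it.

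An alternative is the Participated status in 7.2.5: "Subjects who have met eligibility criteria and have commenced visit 1 procedures". It is simple and already captured, but Visit 1 also includes form completion, so it could admit subjects who were never stimulated. The 11.2 trigger fits the purpose better.

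The cost is a sentence or two in each section, with no change to any procedure. The wider set needs no new data. Assigning events by MAP may need one item on the adverse-event form, because the items listed in 11.2 include start and stop dates but not the MAP in use.
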